8.1.2 Randomization and Stratification

No randomization or stratification will be performed in this study. All patients from all sites will be pooled for analysis.

8.1.3 Populations for Analysis

The populations used for analysis will include the following:

Safety Population: Patients who receive at least 1 dose of MLN9708. The safety population will be used for safety analyses.

DLT-evaluable Population: Patients who receive all Cycle 1 doses of MLN9708 or experience a DLT in Cycle 1. The DLT-evaluable population will be used to determine the MTD.

Organ Response-Evaluable Population: The organ response-evaluable population is defined

as patients who receive at least 1 cycle of MLN9708, have amyloid involvement of at least kidney or heart at baseline, and at least 1 post-baseline organ response assessment.

Hematologic Response-Evaluable Population: The hematologic response-evaluable population is defined as patients who receive at least 1 cycle of MLN9708, have measurable disease at baseline, and at least 1 post-baseline hematologic response assessment.

Plasma PK Analysis Population: Patients who:

- a. Receive full doses of MLN9708 during Cycle 1 without dose reduction or interruptions through the completion of PK sampling
- b. Do not receive any excluded concomitant medications
- c. Have sufficient plasma MLN2238 concentration-time data to permit reliable estimation of plasma PK parameters

Pharmacodynamic Analysis Population: Patients who:

- a. Receive full doses of MLN9708 during Cycle 1 without dose reduction or interruptions
- b. Do not receive any excluded concomitant medications through the completion of pharmacodynamic sampling
- c. Have sufficient whole blood 20S proteasome inhibition-time data to permit reliable estimation of pharmacodynamic parameters

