6.3 Definitions of Dose-Limiting Toxicity (DLT)

6.3.1 DLT Definitions

Although DLTs may occur at any point during treatment, only DLTs occurring during Cycle 1 of treatment must influence decisions regarding dose-escalation, expansion of a dose level, or evaluation of intermediate dose levels. However, DLTs occurring in later cycles may be taken into consideration for dose-escalation decisions, at the discretion of the investigators and sponsors.

Toxicity will be evaluated according to the National Cancer Institute Common Terminology Criteria for Adverse Events (NCI CTCAE), version 4.03.⁽⁵⁸⁾ Toxicity will be evaluated

according to the National Cancer Institute Common Terminology Criteria for Adverse Events (NCI CTCAE), version 4.03. ⁽⁵⁸⁾ DLT will be defined as any of the following AEs that are considered by the investigator to be even possibly related to therapy with MLN9708:

- Any Grade 4 thrombocytopenia (platelets < 25, 000/mm³) lasting at least 7 days.
- Grade 3 thrombocytopenia with clinically significant bleeding, where clinically significant bleeding is defined as a blood loss of > 100 cc or the requirement for a RBC transfusion.
- A platelet count < 10,000/mm³.
- Any Grade 4 neutropenia (ANC < 500/mm³) lasting at least 7 days or Grade 3 febrile neutropenia with fever and/or infection where fever is defined as a temperature $\geq 38.5^{\circ}\text{C}$.
- Grade 2 peripheral neuropathy with pain or Grade 3 or greater peripheral toxicity.
- Any Grade 3 or higher nonhematologic toxicity (in particular, worsening neuropathy, diarrhea despite maximal supportive therapy, life-threatening ventricular arrhythmia or atrial arrhythmia with hemodynamic instability, fluid retention that does not resolve with 3 or 4 days of intravenous diuretic therapy and bedrest, symptomatic congestive heart failure, and hypotension); with the following exceptions: Grade 3 arthralgia/ myalgia and brief (< 1 week) Grade 3 fatigue.
- Grade 3 or greater nausea and/or emesis despite the use of optimal anti-emetic prophylaxis. Optimal anti-emetic prophylaxis is defined as an anti-emetic regimen than employs 5-HT₃ antagonist given according to standard practice.
- A delay of more than 2 weeks in the initiation of Cycle 2 of treatment because of a lack of adequate recovery of MLN9708-related hematological or nonhematologic toxicities.

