- Other MLN9708-related nonhematologic toxicities Grade 2 or greater that, in the opinion of the investigator, requires discontinuation of therapy with MLN9708.

[figure not shown]
Patients who do not receive all doses of MLN9708 in Cycle 1 for reasons other than DLTs will be replaced within the cohort. Patients who receive all doses of MLN9708, yet for unforeseen circumstances recovery of toxicity is not available and safety in Cycle 1 cannot be fully evaluated may be replaced within the cohort.

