7.9 Discontinuation of Treatment With Study Drug, and Patient Replacement

For patients who did not complete treatment by meeting 1 or more of the criteria outlined above, treatment may be discontinued permanently if any of the following criteria are met:

- AE
- Protocol violation
- Study terminated by sponsor
- Withdrawal by patient
- Lost to follow-up
- PD
- Initiation of subsequent therapies
- Progression of amyloid markers (hematologic), see Section 15.9.
- Clinically important decrease in ECOG performance status with organ function deterioration

- Other

At the time of study drug discontinuation, all study procedures outlined for the EOT visit will be completed. The primary reason for study drug discontinuation will be recorded on the electronic case report form (eCRF). Patients who do not meet the DLT-evaluable criteria in the dose-escalation part of the study may be replaced. See Section 8.1.3 for definitions of patient populations of the study.

Patients who are withdrawn from treatment during Cycle 1 for reasons other than DLT may be replaced.

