8. STATISTICAL AND QUANTITATIVE ANALYSES

8.1 Statistical Methods

8.1.1 Determination of Sample Size

A 3 + 3 dose-escalation scheme will be conducted, with 3 to 6 DLT-evaluable patients evaluated at each dose level. It is expected that as many as 30 patients will be enrolled in the dose-escalation part of this study.

Once the MTD/R2PD has been established, the following 2 expansion cohorts will be treated at the MTD or RP2D.

1. Proteasome inhibitor-naive expansion cohort including approximately 8 organ response-evaluable patients. There will be approximately 83% probability of observing at least 2 patients with organ responses among 8 patients based on the binomial probability calculation if the overall organ response rate is 35% for this population. Approximately 10 patients will be enrolled to obtain 8 response-evaluable patients.
2. Proteasome inhibitor-exposed expansion cohort including approximately 14 organ response-evaluable patients. There will be approximately 80% probability of observing at least 2 patients with organ responses among 14 patients based on the binomial probability calculation if the overall organ response rate is 20% for this population. Approximately 16 patients will be enrolled to obtain 14 organ response-evaluable patients.

Because approximately 6 patients in the dose-escalation part of the study will be included in the expansion cohorts, approximately 20 patients will be enrolled in the expansion part of this study.

Overall, as many as 50 patients will be enrolled in this study.

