2.2 DLT-Evaluable Population

The Dose-Limiting Toxicity (DLT)–Evaluable population is defined as patients who receive all Cycle-1 doses of MLN9708 or experience a DLT in Cycle 1 of the dose-escalation phase. The DLT-evaluable population will be used to determine the MTD.

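### DLT-evaluable status requires full Cycle 1 dosing but not completed Cycle 1 safety follow-up, so an incompletely observed patient who is not replaced can count toward the MTD as having no DLT

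*Protocol*

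**What the plan says.** **Definition.** Protocol 8.1.3 takes as DLT-evaluable "Patients who receive all Cycle 1 doses of MLN9708 or experience a DLT in Cycle 1" and adds that "The DLT-evaluable population will be used to determine the MTD". SAP 2.2 uses the same test, limited to dose escalation: "patients who receive all Cycle-1 doses of MLN9708 or experience a DLT in Cycle 1 of the dose-escalation phase". Protocol 8.1.1 plans each level "with 3 to 6 DLT-evaluable patients evaluated at each dose level".

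**Replacement.** Protocol 6.3.1 has two rules.
- For incomplete dosing: "Patients who do not receive all doses of MLN9708 in Cycle 1 for reasons other than DLTs will be replaced within the cohort".
- For a patient who took every dose but for whom "recovery of toxicity is not available and safety in Cycle 1 cannot be fully evaluated may be replaced within the cohort". This rule is discretionary, and it does not say whether the patient leaves the DLT denominator.

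Protocol 7.9 also has two grounds, both discretionary. One is "Patients who do not meet the DLT-evaluable criteria in the dose-escalation part of the study may be replaced". The other covers patients withdrawn from treatment during Cycle 1 for a reason other than DLT.

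**Timing.** Dosing is on Days 1, 8 and 15 of a 28-day cycle. The DLT criteria in 6.3.1 include Grade 4 thrombocytopenia or neutropenia lasting at least 7 days, and "A delay of more than 2 weeks in the initiation of Cycle 2 of treatment because of a lack of adequate recovery".

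**The concern.** Section 6.3.1 treats a certain patient as not fully evaluable, while 8.1.3 and SAP 2.2 class the same patient as evaluable on dosing alone. No other section settles the conflict. SAP section 6 lists no change to this population, and SAP 2.7 says that deviations do not alter population definitions.

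The window between the last dose and the end of DLT assessment is not trivial. A Grade 4 cytopenia that starts after Day 15 needs a further 7 days to qualify. The Cycle 2 delay criterion cannot be judged until about Day 43. A patient lost to follow-up, withdrawn from the study, or started on other therapy inside that window still meets the definition.

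The MTD is a primary endpoint, and under Protocol 6.4 one patient can change the decision at a dose level. The RP2D condition is also stated in terms of DLT-evaluable patients, so it inherits the gap. A patient who occupies a place but whose DLTs could not all be seen makes a dose look safer than it is.

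**Working it through.** **Timing.** Cycle 2 is due on Day 29, and 29 + 14 = Day 43. A delay of more than 2 weeks is therefore known only after Day 43, which is 28 days after the last Cycle 1 dose.

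**The plan's own figures.** The only probabilities stated are for organ response in the expansion cohorts: 83% for at least 2 of 8 at a 35% rate, and 80% for at least 2 of 14 at 20%. Both reproduce (0.831 and 0.802), but neither concerns escalation. The plan gives no operating characteristics for the 3 + 3 part, so the sizes below rest on assumptions.

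**Rule (Protocol 6.4).** A dose is passed with 0 DLTs in 3, or with 1 in 3 followed by 0 in the next 3:

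P(pass) = P(0 of 3) + P(1 of 3) × P(0 of next 3)

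**Assumptions, not in the documents.** The true Cycle 1 DLT rate is p = 0.33. The share of DLTs identifiable only after Day 15 is 30% or 50%. An affected patient's recorded DLT probability is then q = 0.33 × 0.7 = 0.231 or q = 0.33 × 0.5 = 0.165.

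**All patients fully observed.**
- P(0 of 3) = 0.67³ = 0.301
- P(1 of 3) = 3 × 0.33 × 0.67² = 0.444
- P(pass) = 0.301 + 0.444 × 0.301 = 0.434

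**One affected patient in the first three, not replaced.** Here P(0) = (1−p)²(1−q) and P(1) = 2p(1−p)(1−q) + (1−p)²q.
- q = 0.231: P(0) = 0.4489 × 0.769 = 0.345; P(1) = 0.4422 × 0.769 + 0.4489 × 0.231 = 0.444; P(pass) = 0.345 + 0.444 × 0.301 = 0.479
- q = 0.165: P(0) = 0.4489 × 0.835 = 0.375; P(1) = 0.4422 × 0.835 + 0.4489 × 0.165 = 0.443; P(pass) = 0.375 + 0.443 × 0.301 = 0.508

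With one affected patient in each group of three, P(pass) is 0.498 or 0.541.

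**Other true rates**, one affected patient in the first three:

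| True DLT rate | Fully observed | 30% late | 50% late |
|---|---|---|---|
| 20% | 0.709 | 0.737 | 0.756 |
| 33% | 0.434 | 0.479 | 0.508 |
| 50% | 0.172 | 0.214 | 0.242 |

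**Patient replaced but kept in the denominator.** Three or six others are fully observed and the DLT count is unchanged, so the rule of two or more DLTs gives the same decision. Only the tabulated rate moves, for example from 1/3 to 1/4 or from 1/6 to 1/7.

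**Averaged over how often it happens.** Suppose each patient is independently lost after Day 15 with probability L (assumed) and never replaced. The recorded rate is then r = 0.33 × (1 − L × late share). At L = 5% and a 50% late share, r = 0.33 × 0.975 = 0.322 and P(pass) = 0.451, a rise of 1.6 points. Across the 30% to 50% late shares, the rise is:

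| L | Rise in P(pass), points |
|---|---|
| 2% | 0.4–0.6 |
| 5% | 1.0–1.6 |
| 10% | 1.9–3.3 |

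**The case against.** A reader might infer that unobserved patients routinely dilute the DLT rate that sets the MTD. The documents do not support that, for these reasons.

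- **Stopping treatment is not loss of observation.** Schedule of Events footnotes b and d require patients who stop after Cycle 1 to complete the end-of-treatment assessments, at least 30 days after the last dose or before new antineoplastic therapy. Protocol 10.3 collects adverse events for 30 days after the last dose unless such therapy starts. Day 15 + 30 = Day 45, which is past Day 43. Protocol 6.5.1 also has toxicity evaluated weekly.
- **Many toxicity-driven exits already count.** Under 6.3.1, related nonhematologic toxicity of Grade 2 or higher that the investigator judges to require stopping MLN9708 is itself a DLT.
- **Replacement has two routes.** Besides 6.3.1, the second ground in 7.9 covers withdrawal from treatment in Cycle 1 whether or not the patient meets the DLT-evaluable criteria.
- **The stopping rule is a count**, so a replaced patient does not change it.
- **No section scores missing safety data as DLT-free.** Protocol 8.1.4 bars imputation. That such a patient ends up with no DLT on record is an inference from the definition.
- **There are backstops.** The RP2D draws on 6 evaluable patients and on later-cycle data, and about 20 more patients are then treated at the chosen dose.

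All of this stands, and it makes the affected group small: fully dosed patients who are lost, leave the study, or start other therapy early. It does not close the gap. Protocol 7.10 says no new information is collected after study withdrawal, although every effort is made to follow for safety. Every replacement route that reaches a fully dosed patient is optional. The six patients behind the RP2D are counted under the same definition.

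**Conclusion.** The inconsistency is real and bears on a primary endpoint. As written, a fully dosed but incompletely observed patient is DLT-evaluable. If that patient is not replaced, the patient can occupy one of the 3 or 6 places with no DLT recorded, and the resulting error favours escalation.

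The rise from 43% to 48%–51% is illustrative. It is conditional on one such unreplaced patient in the first three, a 33% true DLT rate, and a 30% to 50% late share, none of which the documents supply. It should not be read as the expected effect. With assumed loss rates of 2% to 10% and no replacement, the rise is about 0.4 to 3.3 points, and replacement would reduce it further. Calling these patients unobserved would also be too strong, since a fully dosed patient received drug through Day 15 and any DLT already seen still counts.

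The point should be fixed because it is cheap and the population determines the MTD. It does not put the dose-finding as a whole in doubt.

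**What to change.** 1. In Protocol 8.1.3 and SAP 2.2, define DLT-evaluable as having a Cycle 1 DLT, or having received all Cycle 1 doses *and* having enough safety follow-up to judge the Cycle 1 DLT criteria, including resolution of any delay in starting Cycle 2.
2. State in both places that a patient who fails this definition is excluded from the denominator used for the MTD.
3. Reconcile 6.3.1 and 7.9 with that definition. At present 6.3.1 says incompletely dosed patients *will* be replaced, 7.9 says patients who are not DLT-evaluable *may* be, and 6.3.1 says fully dosed but not fully evaluable patients *may* be. Use one rule in both sections. Once such patients are excluded, the requirement in 8.1.1 for 3 to 6 DLT-evaluable patients per level already implies replacement whenever a cohort would fall short.

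The cost is a sentence or two in each document and an occasional extra replacement, which 6.3.1 already permits. It adds no visits beyond the end-of-treatment and 30-day follow-up already scheduled.

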8.1.4 Procedures for Handling Missing, Unused, and Spurious Data

All available efficacy and safety data will be included in data listings and tabulations. No imputation of values for missing data will be performed.

Data that are potentially spurious or erroneous will be examined according to standard data management operating procedures.

8.1.5 Demographic and Baseline Characteristics

Demographic and baseline characteristics will be summarized by dose levels of MLN9708 and expansion cohorts. Data to be evaluated will include at least age, sex, race, weight, height, etc. Components of disease severity assessment in addition to relevant patient and disease assessments and laboratory parameters will be presented if appropriate.

8.1.6 Efficacy Analysis

Standard response criteria will be used in this study.^(53, 54) The patients treated at doses other than the dose in the expansion cohorts may be combined together for analysis and for presentation in the tables and figures.

The efficacy parameters include the organ response rate and organ improvement rate, overall hematologic response rate, time to hematologic and organ response, duration of hematologic and organ response, time to hematologic and organ response, hematologic and organ disease free progression, and 1-year survival rate.

The organ response and improvement rate will be analyzed based on the organ response-evaluable population. Estimates of the organ response rate will be presented with 2-sided 95% exact binomial confidence intervals.

The hematologic response rate will be analyzed based on the hematologic response-evaluable population and presented with 2-sided 95% exact binomial confidence interval.

Time to organ or hematologic response is defined as the time from the date of the first dose of MLN9708 to the date of first documentation of a confirmed organ or hematologic response, respectively.

Duration of organ or hematologic response is defined as the time from the date of first documentation of a confirmed organ or hematologic response to the date of confirmed organ or hematologic disease progression, respectively.

Time to organ or hematologic disease progression is defined as the time from the date of the first dose of MLN9708 to the date of first documented organ or hematologic disease progression.

[figure not shown]
Organ or hematologic disease progression free survival is defined as the time from the date of the first dose of MLN9708 to the date of confirmed organ or hematologic disease progression or death, respectively.

One-year survival is defined as the patient survival probability at 1 year after the date of first dose of MLN9708.

Time to response, duration of response, time to progression, PFS, and survival may be analyzed using standard survival analysis techniques based on Kaplan-Meier estimates if appropriate.

8.1.6.1 Exploratory Efficacy Endpoints and Analysis

CCI

8.1.7 Pharmacokinetics, Pharmacodynamics, and Exploratory Analyses

Pharmacokinetic Analysis

[figure not shown]
PK analysis will be based on concentrations of MLN2238, the complete hydrolysis product of MLN9708.

Individual and mean plasma and whole blood concentration data will be plotted over time. Summary tables will be presented for the plasma and whole blood concentration data. Plasma and whole blood PK parameters will be estimated using noncompartmental analysis methods. The PK parameters calculated for individual plasma MLN2238 concentration-time data and whole blood MLN2238 concentration-time data will include, but are not limited to: C_{max} , T_{max} , and AUC_{tau} . PK parameters will be summarized using descriptive statistics.

Pharmacodynamic Analysis

[figure not shown]
Individual and mean whole blood 20S proteasome inhibition data will be plotted over time. Summary tabulations will be presented for the whole blood 20S proteasome inhibition data. Pharmacodynamic parameters of whole blood 20S proteasome inhibition will be estimated using noncompartmental analysis methods. The pharmacodynamics parameters calculated for individual whole blood 20S proteasome inhibition-time data will include, but are not limited to: maximum inhibition (E_{max}) and time of occurrence of E_{max} (TE_{max}). Pharmacodynamic parameters will be summarized using descriptive statistics.

CCI

Tumor Biomarker Analysis

CCI

8.1.8 Safety Analysis

Summary tabulations will be presented that will display the number of observations, mean, standard deviation, median, minimum, and maximum for continuous variables, and the number and percent per category for categorical data.

The incidence of DLT may be tabulated for each dose group. In addition, to assess the relationship between toxicities and MLN9708 dose, the preferred term of individual toxicities may be summarized by their frequency and intensity for each dose group. The DLT-evaluable population will be used for the analysis of DLT. DLT will also be listed for each dose group.

Safety will also be evaluated by the incidence of treatment emergent AEs, severity and type of AEs, and by changes from baseline in the patient's vital signs, weight, and clinical laboratory results using the population evaluable for safety. Exposure to study drug and reasons for discontinuation will be tabulated.

Treatment-emergent events will be tabulated. Treatment emergent is defined as any AE that occurs after administration of the first dose of study drug and up through 30 days after the last dose of study medication, any event that is considered drug related regardless of the start date of the event, or any event that is present at baseline but worsens in severity after baseline or is subsequently considered drug related by the investigator. AEs will be

tabulated according to the Medical Dictionary for Regulatory Activities (MedDRA) by system organ class, high-level terms, and preferred terms and will include the following categories:

- Treatment-emergent AEs
- Drug-related treatment-emergent AEs
- Grade 3 or higher treatment-emergent AEs
- Grade 3 or higher drug-related treatment-emergent AEs
- Treatment-emergent AEs resulting in study drug reduction
- Treatment-emergent AEs resulting in study drug discontinuation
- SAEs

The most commonly reported treatment-emergent AEs (ie, those events reported by $\geq 10\%$ of all patients) will be tabulated by high level term and preferred term.

Descriptive statistics for the actual values and/or change from baseline of clinical laboratory parameters will be presented for all scheduled measurements over time. Mean laboratory values over time will be plotted for key laboratory parameters.

Descriptive statistics for the actual values and changes from baseline of vital signs, weight, and ECOG scores will be tabulated by scheduled time point.

Shift tables for laboratory parameters will be generated based on changes in NCI CTCAE Grade from baseline to the worst post baseline value. Graphical displays of key safety parameters, such as scatter plots of baseline versus worst post baseline values, may be used to understand the MLN9708 safety profile.

All concomitant medications collected from screening through the study period will be classified to preferred terms according to the World Health Organization (WHO) drug dictionary.

Additional safety analyses may be performed to most clearly enumerate rates of toxicities and to further define the safety profile of MLN9708.

